Problem statement	
Postoperative care of patients undergoing endoscopic sinus surgery (ESS) is important both to minimize discomfort for the patients and to obtain the optimal long-term outcomes. Postoperative sinonasal cavity debridement has been advocated to prevent potential synechiae and sinus ostial stenosis, as well as to improve patient symptoms. Removal of old blood, nasal secretions, crusting, and unabsorbed packing are thought to reduce the inflammatory load, minimize potential for scarring, and allow for improved access of topical medications. However, the debridement procedure can cause bleeding, pain, and discomfort which may interfere with the effective execution of postoperative care.
 
Postoperative formation of adhesions, scarring, synechiae, middle turbinate lateralization, ostial stenosis and edema are major concerns often addressed by the placement of bioresorbable packing intraoperatively. Bioresorbable packing has been demonstrated to decrease the incidence of adhesions and bleeding while improving patient comfort compared to no packing at all. However, bioresorbable nasal dressings, such as PosiSep X, oftentimes have not dissolved by the time of the first postoperative debridement 1-2 weeks after the surgery and therefore need to be removed. The removal of bioresorbable packing during postoperative debridements is usually an uncomfortable experience for the patient. An ideal nasal dressing would optimize both patient comfort as well as wound healing.
 
PuraSinus is a novel topical haemostatic agent based on nanotechnologies in the form of a transparent hydrogel suitable for endoscopic use and for which the use in sinonasal surgery could achieve these various goals. The potential of PuraSinus to enhance endoscopic mucosal wound healing may play a role in optimizing patient comfort during postoperative debridements after ESS. However, clinical evidence on its effectiveness in ESS is limited.
 
We aim to perform a randomized controlled trial to evaluate the efficacy of PuraSinus in improving patient comfort during postoperative debridements among patients who underwent ESS.

Type of Study	prospective, randomized, controlled, single-blinded study.
Study Participants	Patients with chronic rhinosinusitis undergoing bilateral endoscopic total ethmoidectomy receiving standard of care and PosiSep X on one side and PuraSinus in addition to standard of care on the other side. The patients are their own control.

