2.0 OBJECTIVES AND PURPOSE

The objective of this study is to assess the efficacy of PuraSinus in improving postoperative outcomes in patients who undergo endoscopic sinus surgery for chronic rhinosinusitis compared to standard postoperative absorbable packing.

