2.1 Primary objective

- To investigate the efficacy of PuraSinus in reducing patient pain during postoperative debridement after endoscopic sinus surgery compared to bioresorbable packing.

2.2 Secondary objectives:

- To assess the time needed to perform postoperative debridements in patients with PuraSinus in their ethmoid cavity after endoscopic sinus surgery
- To assess the efficacy of PuraSinus in preventing postoperative complications from endoscopic sinus surgery (adhesions, bleeding, crusting, edema)
- To assess the amount of PuraSinus retained in the ethmoid cavity postoperatively
- To assess the need for further intervention postoperatively in patients

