6.0 STRATIFICATION/DESCRIPTIVE FACTORS/RANDOMIZATION SCHEME

6.1 The patient will undergo a bilateral operation. At the end of the surgery, hemostasis will be performed with PosiSep X placed in the ethmoid cavity on one side and PuraSinus in the other ethmoid cavity. The randomization will occur using the envelope method to determine which ethmoid cavity will receive PuraSinus and which ethmoid cavity will receive PosiSep X.

Prior to the start of this trial, a randomization list will be generated and sealed opaque envelopes will be created for each participant in the study. Each envelope will instruct which ethmoid cavity (RIGHT or LEFT) will receive PuraSinus. During the surgery, after a total ethmoidectomy has been performed bilaterally by the surgeon, the research coordinator or research staff will open the assigned envelope and have the surgeon read which side the PuraSinus should be applied to. The contralateral ethmoid cavity will receive PosiSep X. The research staff or research coordinator will verify that the intervention (PuraSinus) was applied to the assigned ethmoid cavity.

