10.5 Amount of residual PuraSinus or bioresorbable dressing in ethmoid cavity

At 1 week after surgery, the amount of residual PuraSinus or PosiSep X in the ethmoid cavity will be measured as none, less than 50% of ethmoid cavity, or 50% or greater of ethmoid cavity.

10.6 The need for further intervention postoperatively at week 4

At 4 weeks after surgery, a recorded nasal endoscopy will be performed of each participant's ethmoid cavity and reviewed by an independent, blinded rhinologist to evaluate whether the participant required a postoperative intervention.

A post-operative intervention is a composite endpoint that includes:

- Surgical intervention required to debride obstructive adhesions or scar tissue formation
- Oral steroid intervention is warranted to resolve recurrent inflammation or polypoid edema

11.0 SPECIAL INSTRUCTIONS:

Participant remuneration: Participants in the clinical trial will receive remuneration in the form of \$90 in gift cards. Participants will receive a \$30 VISA gift card after each postoperative visit (week 1, week 4, and week 12) for a total of \$90. The remuneration is to compensate the patient for parking fees and time associated with participating in all aspects of this trial.

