12.0 DATA COLLECTION AND MONITORING

12.1 Data collection forms

Data will be recorded onto a dedicated data collection form following the initial surgical procedure where PuraSinus and bioresorbable packing were used. The data on these anonymized forms will then be entered onto a secure password protected electronic database (REDCap) with appropriate back up systems and security protocols in place. No patient identifiable data will be stored on the database.

Endoscopic video data will be coded by the patient's research ID and laterality (right vs. left). No patient identifiable data will be used to label the video files, which will be stored on a secure university online database (Microsoft OneDrive).

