13.2 Statistical analysis

The sample will be described by demographic and clinical characteristics, summarizing continuous variables by mean (SD) and categorical variable by frequency (percent). All trial outcome comparisons will be tested at a two-sided p-value of 0.05.

Primary objective: To investigate the efficacy of PuraSinus in reducing patient pain during postoperative debridement after endoscopic sinus surgery compared to PosiSep X.

The primary outcome of pain at 1-week debridement, evaluated on a 1-10 scale, will be compared between interventions using a Wilcoxon signed rank test (paired test). The median and interquartile range of the pain score will be summarized for each intervention. To consider side (right/left), a generalized linear mixed effects model will analyze the pain score as a dependent variable, with a random intercept for participant; independent variables will include randomized intervention, side, and an interaction of intervention-by-side (testing if the intervention effect may differ by side).

Secondary objectives:

- To assess the time needed to perform postoperative debridements in patients with PuraSinus in their ethmoid cavity after endoscopic sinus surgery
- To assess the efficacy of PuraSinus in preventing postoperative complications from endoscopic sinus surgery (adhesions, bleeding, crusting, edema)
- To assess the amount of PuraSinus retained in the ethmoid cavity postoperatively
- To assess the need for further intervention postoperatively in patients

Continuously measured secondary trial outcomes (time required for debridement; Lund-Kennedy Endoscopy score) will be compared between interventions using Wilcoxon signed rank and generalize mixed effects model as described above. Amount of bioresorbable dressing retained will be presented as proportions, with 95% confidence intervals (in the categories of none, <50%, ≥50%). Bleeding during debridement and adhesions will be presented as proportions. The need for further intervention will also be presented as proportion (with 95% confidence interval) of participants required further surgical or oral steroid intervention.

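### Need for further intervention is judged and reported per participant, although every participant receives both products, so the planned proportion cannot show a PuraSinus versus PosiSep X difference

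*Combined protocol and SAP*

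**What the plan says.** The design is within-patient. The synopsis states "The patients are their own control", and section 6.1, after assigning one side to PuraSinus, adds "The contralateral ethmoid cavity will receive PosiSep X". The ethmoid cavity is therefore the randomised unit, and the overall aim in section 2.0 is efficacy "compared to standard postoperative absorbable packing".

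For this outcome, section 10.6 has the week 4 endoscopy "reviewed by an independent, blinded rhinologist to evaluate whether the participant required a postoperative intervention". The outcome is a composite of surgical debridement of obstructive adhesions or scar, and an oral steroid for recurrent inflammation or polypoid edema. Section 13.2 then says: "The need for further intervention will also be presented as proportion (with 95% confidence interval) of participants required further surgical or oral steroid intervention".

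The matching secondary objective in section 2.2 is "To assess the need for further intervention postoperatively in patients", which names no comparator. By contrast, sections 10.1 and 10.2 record pain and debridement time for each cavity, and section 13.2 compares pain, time and the Lund-Kennedy score between interventions.

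**The concern.** When everyone receives both products, a participant either needs further intervention or does not, and that answer belongs to neither product. The planned proportion is the same whether the need arises on the PuraSinus side, on the PosiSep X side, or on both. No section defines a side-level result, a rule for attributing need to a side, or a paired binary analysis for this outcome.

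A larger sample would not help, because the contrast is not identified from the data as recorded. The split-nose design would allow a within-patient comparison of this composite, and the plan does not use it.

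**Working it through.** **The plan's own figures.** The documents give no rate, target difference or power for this outcome. The only computed design figure is 83% power for the primary pain test (section 13.1: n = 30, difference 2, SD 3.5, two-sided 0.05). Paired t power with n scaled by 3/π (30 to 28.65) gives 0.839, and simulation of the exact signed rank test gives 0.840. That is close to the stated figure, and the present point does not depend on it.

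**Inputs.** n = 30 (section 13.1); two-sided 0.05 (section 13.2). All event counts below are assumptions, as is a week 4 read for all 30 participants. Section 10.0 requires only week 1 attendance for inclusion in the analysis.

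**What is and is not identified.** Let a = participants needing intervention on both sides, b = on one product's side only, c = on the other product's side only.

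- Planned figure: (a + b + c)/n
- Product difference: (b - c)/n

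If a + b + c = k, then b - c can be any whole number from -k to +k. With k = 6 the difference can lie anywhere from -6/30 to +6/30, that is -20 to +20 points.

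**Planned output (Clopper-Pearson 95% CI).**

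- 3/30 = 10% (2.1% to 26.5%)
- 6/30 = 20% (7.7% to 38.6%)
- 9/30 = 30% (14.7% to 49.4%)

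**What side-level recording would show for the same 6/30.** Exact McNemar p = 2 × P(Bin(b + c, 0.5) ≤ min(b, c)), capped at 1. The interval is Bonett-Price: with p1 = (b + 1)/(n + 2) and p2 = (c + 1)/(n + 2), the limits are (p1 - p2) ± 1.96 × √{[p1 + p2 - (p1 - p2)²]/(n + 2)}.

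Worked case, b:c = 6:0. p1 = 7/32 = 0.21875 and p2 = 1/32 = 0.03125, so p1 - p2 = 0.1875. The standard error is √[(0.25 - 0.0352)/32] = 0.0819, giving limits 0.027 and 0.348. The test gives p = 2 × (1/2)^6 = 0.031.

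| a | b:c | Difference (points) | 95% CI | p |
|---|---|---|---|---|
| 0 | 6:0 | 20.0 | 2.7 to 34.8 | 0.031 |
| 0 | 5:1 | 13.3 | -4.3 to 29.3 | 0.22 |
| 0 | 4:2 | 6.7 | -10.9 to 23.4 | 0.69 |
| 0 | 3:3 | 0 | -17.3 to 17.3 | 1.0 |
| 2 | 4:0 | 13.3 (6/30 vs 2/30) | -1.9 to 26.9 | 0.125 |

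Reversing a split changes the sign. Every row gives the same planned output of 20%.

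**Power of a side-level comparison.** Exact McNemar, n = 30, full enumeration over assumed discordant rates:

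- 5% vs 15%: 0.099
- 5% vs 20%: 0.235
- 5% vs 30%: 0.570

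**The case against.** **The objective is descriptive.** Section 2.2 names no comparator, the objective, definition and analysis all use the patient as the unit, and the hypotheses in section 1.0 do not mention further intervention. This is fair as far as it goes. But the debridement-time objective also names no comparator, and section 13.2 still compares time between interventions. The wording of 2.2 does not explain why this outcome is handled differently.

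**Side-level judging may be intended.** Section 10.6 speaks of recording each participant's ethmoid cavity, and section 12.1 codes video files by side. That describes what is filmed. The judgement clause in the same sentence names the participant, and 13.2 reports on that unit. Side-level judging is feasible but not specified.

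**Oral steroid is systemic.** This stands in part. Attribution is possible only through the finding that prompts the steroid, and that overlaps with the edema and polyp items already scored by cavity. The surgical component has no such difficulty.

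**Low power and limited consequence.** This stands. Few events are likely to be discordant, and losses before week 4 would reduce n. Section 13.2 still compares the Lund-Kennedy score between interventions, though it names no component-level comparison, and adhesions are also read at week 4. The missing paired binary analysis is not peculiar to this outcome: adhesions and bleeding are given only as proportions. This outcome differs in that its stated unit rules out a product split.

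**Conclusion.** The concern holds. As written, this secondary composite gives one participant-level proportion that fits any product difference from minus to plus its own size (-20 to +20 points for an assumed 6 of 30). It cannot contribute to the comparison with PosiSep X.

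The conclusion follows from the unit named in 10.6 and 13.2 and from the within-patient design, not from the assumed counts, which only illustrate size. The loss is confined to the product split of this one outcome; the primary endpoint and sample size are untouched. Once repaired, the comparison is identified but imprecise. Among the illustrated splits of six events only 6:0 reaches p < 0.05, so it should be presented as estimation.

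**What to change.** **Section 10.6.** Suggested text: 'The blinded reviewer records yes or no separately for the left and right cavity for each component: (a) obstructive adhesions or scar requiring surgical intervention; (b) recurrent inflammation or polypoid edema for which oral steroid is judged warranted, attributed to the cavity or cavities showing the finding. Both sides may be yes.'

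**Section 13.2.** Suggested text: 'The proportion of cavities needing further intervention is reported for each product, overall and by component, with the paired risk difference and 95% CI. An exact McNemar test is supportive only. With 30 participants this comparison is descriptive. The participant-level proportion is kept as a descriptive line.'

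If the team does not accept side attribution for the steroid component, it can report that component per participant and split only the surgical component by product.

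**Cost.** Four yes/no answers per participant (two components, two sides) replace one judgement at the existing week 4 read, with no extra visit or reader. If the videos have already been read, a blinded re-read of the side-coded files can supply the answers. The downside is that side attribution of a systemic steroid rests on the reader's judgement and may partly repeat the edema and polyp scores.

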14.0 REGISTRATION GUIDELINE

14.1 Participants in this study will be registered at the preoperative visit prior to their surgery or the day of their surgery in the preoperative area. All participants will receive the intervention (PuraSinus) in one

ethmoid cavity at the end of the ESS procedure which will be randomized in the operating room with the envelope method.

14.2 All registered participants will complete the following forms prior to participation in the study:

- Informed Consent
- Registration/Eligibility Worksheet
- Demographic questionnaire

Note: At the time of registration, two copies of a signed and dated patient Informed Consent form must be available (one copy for the patient; and the other for the PI's file).

15.0 BIOHAZARD CONTAINMENT

No biohazard materials will be handled at any time during this study.

16.0 ETHICAL AND REGULATORY CONSIDERATIONS

All institutional and Federal regulations concerning the Informed Consent form will be fulfilled. The study will be conducted in adherence to ICH Good Clinical Practice. The sponsor and investigator(s) shall avoid improper influence or inducement of the study patient, study coordinator, the clinical investigator(s) or other parties participating in or contributing to the clinical investigation.

